10.1.3 Exposure during the initial and maintenance period for BKZ Set

Definitions for study medication duration (days) and time at risk (days) through initial and maintenance treatment period are provided as follows:

For subjects randomized to BKZ Q4W/Q4W:

Study medication duration (days)

- Date of last dose of bimekizumab – date of first dose + 28 days

Note: If date of last dose of bimekizumab+ 28 days extends to a date beyond the final visit date (including PEOT, but not including SFU), then this calculation reverts to:

- Final visit date (including PEOT, but not including SFU) – date of first dose + 1.

Note: For subjects who die, if date of last dose of bimekizumab+ 28 days extends to a date beyond the date of death, then this calculation reverts to:

- Date of death – date of first dose + 1.

Time at risk (days):

- For subjects who continue into an open-label study (and, therefore, do not have the SFU visit in the feeder study): Final visit date – date of first dose + 1.
- For subjects who die prior to the final visit: Date of death – date of first dose + 1.
- For all other subjects, use the minimum of the following:
 - Date of last dose – date of first dose + 140 days.
 - Date of last clinical contact – date of first dose + 1.

Note: This group could include subjects who discontinue early, subjects who complete the Maintenance Period as scheduled but choose not to continue into an open-label study, or subjects who are ongoing in the SFU period at the time of the data snapshot.

For subjects randomized to BKZ Q4W/Q8W:

Study medication duration (days)

- Initial Treatment Period (attributed to BKZ Q4W)
 - Date of last dose of bimekizumab in the Initial Treatment Period – date of first dose in the Initial Treatment Period + 28 days

Note: If date of last dose of bimekizumab in the Initial Treatment Period + 28 days extends to a date beyond the date of the first dose in the Maintenance Treatment Period, then this calculation reverts to:

- Date of first dose in the Maintenance Treatment Period – date of first dose in the Initial Treatment Period + 1.

Note: For subjects who die during the Initial Period, if date of last dose of bimekizumab in the Initial Treatment Period + 28 days extends to a date beyond the date of death, then this calculation reverts to:

- Date of death – date of first dose in the Initial Treatment Period + 1.

- Maintenance Treatment Period (attributed to BKZ Q8W)

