10.2.1 Data considerations

Treatment-emergent AEs (TEAEs) are defined as those AEs that have a start date on or following the first dose of study treatment through the final dose of study treatment + 140 days

(covering the 20-week SFU period). If it is not possible (due to partial dates) to determine whether or not an AE is treatment-emergent then it will be assumed to be a TEAE.

The rules for imputing partial start or stop dates are outlined in Section 4.2.1.2.

If the intensity of an adverse event is unknown, it is considered as severe. If the relationship to study drug is missing, it is considered as related.

AEs will be presented as “number of subjects (percentage of subjects) [number of events]”. In this style of output, “[number of events]” will include all cases of an AE including repeat occurrences in individual subjects, while “number of subjects” will count each subject only once.

Subject time at risk represents the time a subject is at risk for having an AE. The definitions for subject time at risk (in days) are outlined in Section 10.1. These definitions will be used for exposure-adjusted AE summaries.

Selected AE summaries will include the exposure adjusted incidence rate (EAIR) with associated 95% confidence interval and the exposure adjusted event rate (EAER).

The EAIR is defined as the number of subjects (n) with a specific AE adjusted for the exposure and will be scaled to 100 patient-years:

$$EAIR = 100 \times n / \sum_{i=1}^N (T_{Exp(i)})$$

Where $T_{Exp(i)}$ is the exposure time and N is the number of subjects at risk.

If a subject has multiple events, the time of exposure is calculated to the first occurrence of the AE being considered. If a subject has no events, the total time at risk is used.

Exact Poisson 95% confidence intervals for incidence rates are calculated using the relationship between the Poisson and the Chi-square distribution (Ulm, 1990; Fay and Feuer, 1997):

$$LCL = \chi^2_{2n, \alpha/2} / 2$$

$$UCL = \chi^2_{2(n+1), \alpha/2} / 2$$

where n is the number of subjects with a specific AE for the incidence rate of interest and is the basis for the number of the degrees of freedom for the chi-square quantile for the upper tail probability χ^2 .

The EAER will be the number of AEs including repeat occurrences in individual subjects divided by the total time at risk scaled to 100 patient-years and calculated using:

$$EAER = 100 \times N_{AE} / \sum_{i=1}^N (T_{Risk(i)})$$

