where N_{AE} is the total number of AEs, T_{Risk} is the time at risk for each subject, and N is the total number of subjects at risk.

No confidence interval will be computed for EAER.

Selected summaries for the subjects who switch from adalimumab to bimekizumab will be presented by time of onset (≤ 70 days or > 70 days from the final dose of adalimumab). Only events starting after the first dose of bimekizumab will be included.

70 days was chosen as it is approximately equal to five half lives of adalimumab.

Selected summaries, as specified in Section 10.2.2, will include the risk difference between bimekizumab and adalimumab. The risk difference is calculated as:

$$RD = IP_{BKZ} - IP_{ADA}$$

where IP_{BKZ} is the incidence proportion for the bimekizumab-treated group and IP_{ADA} is the incidence proportion for the adalimumab group. Note that incidence proportion simply refers to the percentage of subjects within the specified treatment group that experienced a given adverse event.

The standard error for the risk difference is calculated as follows:

$$SE_{RD} = \sqrt{\left(IP_{BKZ} \times \left(\frac{1 - IP_{BKZ}}{n_{BKZ}} \right) \right) + \left(IP_{ADA} \times \left(\frac{1 - IP_{ADA}}{n_{ADA}} \right) \right)}$$

where n_{BKZ} is the number of subjects in the bimekizumab-treated group and n_{ADA} is the number of subjects in the adalimumab group.

The corresponding confidence interval for the risk difference is as follows:

$$CI_{RD} = RD \pm Z_{1-\alpha/2} \times (SE_{RD})$$

where $Z_{1-\alpha/2}$ is the Z statistic for the corresponding level of alpha. For the risk difference confidence intervals calculated in this SAP, 1.96 will be used (corresponding to a two-sided alpha of 0.05 and 95% confidence interval). Risk difference and the corresponding confidence interval will be presented as a percentage.

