The following summary will be provided through initial and maintenance treatment period for the BKZ Set:

- Incidence of TEAEs per 100 subject years by SOC, HLT, and PT and by Time of Onset Relative to Anti-bimekizumab Antibody Status

In addition, all summaries of TEAEs based on “100 subject years” should include EAIR (with 95% confidence interval) and EAER.

The tables with risk differences will also be accompanied by figures (dot plots) which show the incidence of the adverse events and corresponding 95% risk difference confidence intervals. These will be ordered by descending order of risk difference (bimekizumab vs adalimumab).

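### The adverse-event table by onset relative to antibody status splits events at positivity but not person-time, so its before and after rates are not comparable

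*SAP*

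**What the plan says.** SAP 10.2.2 lists one table for the BKZ Set, over the initial and maintenance periods: "Incidence of TEAEs per 100 subject years by SOC, HLT, and PT and by Time of Onset Relative to Anti-bimekizumab Antibody Status". It adds that every summary expressed per 100 subject years "should include EAIR (with 95% confidence interval) and EAER".

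SAP 10.2.1 supplies the denominators. It refers to the subject time at risk in Section 10.1 and states: "These definitions will be used for exposure-adjusted AE summaries". The EAER denominator is the sum over subjects of a quantity that "is the time at risk for each subject". For EAIR, when a subject has multiple events, "the time of exposure is calculated to the first occurrence of the AE being considered"; otherwise, "If a subject has no events, the total time at risk is used".

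Section 10.1.3 sets time at risk for the combined periods. For subjects entering the open-label study it is "Final visit date – date of first dose + 1". For most others it is the smaller of "Date of last dose – date of first dose + 140 days" and the time to last clinical contact. Sections 10.1.3 and 10.1.4 divide person-time by period and regimen (for example, Q4W time and Q8W time in the Q4W/Q8W arm). They do not divide it by antibody status.

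SAP 9.3.2 uses the date of first treatment-emergent positivity for a Kaplan-Meier analysis, and a separate rule of at least two positive time points for efficacy subgroups. Neither is linked to this table.

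**The concern.** Antibody status changes during follow-up. An event can fall after positivity only in the person-time that follows the first positive sample, and before it only in the person-time that precedes it. If each category's events are divided by time that also covers the other category, both rates are too low, by amounts that depend on when positivity was detected. The contrast between them then reflects detection timing rather than any effect of antibodies.

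I found no other planned table that relates antibody formation to adverse events; SAP 9.3.2 relates antibodies to drug concentration and PASI. Hypersensitivity is a pre-specified safety topic (protocol 12.1.1.4; SAP 10.2.3.7). An artificial excess after positivity could be read as antibody-mediated harm, and an artificial deficit could hide a real one.

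**Working it through.** The documents give no figure for this table, so there is none to reproduce. The check applies the SAP's formulas to a case with no antibody effect.

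**Inputs from the documents**
- Time at risk T is about 56 weeks for a bimekizumab-randomized subject who enters the open-label study. It is about 52 + 140/7 = 72 weeks for one whose last dose is at Week 52 and who does not (SAP 10.1.3).
- Possible weeks s of first positivity during treatment are the post-baseline samples at Weeks 4, 8, 12, 16, 20, 24, 36 and 48 (SAP 9.3.2). Week 56 is also sampled but leaves no later time in a 56-week follow-up.

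**Assumptions not in the documents**
- A constant event rate L, the same before and after positivity.
- The values of s and L.
- A before/after layout within ever-positive subjects.

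**EAER, unsplit denominator**
- Before: L·s/T. After: L·(T − s)/T. Ratio after:before: (T − s)/s. The correct ratio is 1.

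| First positive | Before ÷ true (T = 56) | After ÷ true (T = 56) | Ratio, T = 56 | Ratio, T = 72 |
|---|---|---|---|---|
| Week 8 | 0.143 | 0.857 | 6.0 | 8.0 |
| Week 16 | 0.286 | 0.714 | 2.5 | 3.5 |
| Week 24 | 0.429 | 0.571 | 1.33 | 2.0 |
| Week 36 | 0.643 | 0.357 | 0.56 | 1.0 |
| Week 48 | 0.857 | 0.143 | 0.17 | 0.5 |

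The direction reverses at T/2, that is Week 28 of 56 or Week 36 of 72.

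In a simulation of 200,000 subjects (true rate 200 per 100 subject years, T = 56), spreading first positivity evenly over the samples from Weeks 4 to 16 gave 35.8 before and 164.2 after, a ratio of 4.6. Spreading it over all eight samples gave 1.67. Weeks 24, 36 and 48 only gave 0.56.

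**EAIR, unsplit clock from first dose**
- Before: p = 1 − exp(−Ls); expected exposure = [1 − exp(−Ls)(1 + Ls)]/L + (1 − p)·T.
- After, with D = T − s: p = 1 − exp(−LD); expected exposure = p·s + [1 − exp(−LD)(1 + LD)]/L + (1 − p)·T.
- The rate is p divided by expected exposure. For T = 56:
  - True rate 5 per 100 subject years: 1.4 before and 3.6 after at Week 16 (ratio 2.5); ratio 0.55 at Week 36. This is close to EAER.
  - True rate 300: 118.9 before and 148.3 after at Week 16 (ratio 1.25); 257.3 and 74.5 at Week 36 (ratio 0.29). For very common events the distortion is smaller with early positivity, but not with late positivity.

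**Placement of never-positive subjects** (EAER, T = 56, 40% of subjects first positive at Week 16)
- Events before or never positive are proportional to 0.4 × 16 + 0.6 × 56 = 40. Events after are proportional to 0.4 × 40 = 16.
- With all subjects' time under both columns, the ratio is 16/40 = 0.40.
- With only positive subjects' time under the after column, it is (16/22.4)/(40/56) = 1.00. This is a coincidence of the inputs: 20% positive at Week 16 gives 0.83, and 50% positive at Week 8 gives 1.50.

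**Adalimumab switchers.** Bimekizumab time runs from Week 24, so T is about 32 or 48 weeks. The first post-switch antibody result is at Week 36, that is s = 12. The ratios are 20/12 = 1.67 and 36/12 = 3.0.

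**With person-time split at s**, EAER before is Ls/s = L and EAER after is L(T − s)/(T − s) = L. In the simulation with positivity at Weeks 4 to 16, the split rates were 200.6 and 199.8. EAIR with the clock restarted at s also returned the true rate in both categories.

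**The case against.** The table is a single bullet with no defined columns, onset date or denominator of its own. Section 10.2.1 describes time at risk as time in which a subject could have an adverse event, which could be taken to mean time in category. The SAP does split time between regimens, so a programmer might split it here too, and table shells that we do not have might say so. This stands in part: the columns are undefined, so no layout can be called the planned one. It does not remove the problem, because 10.2.1 applies the Section 10.1 definitions to exposure-adjusted summaries without exception. Where the SAP wants person-time split by regimen, it writes the split out.

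A reader might infer from the Week 8 and Week 16 ratios that adverse events will look several times more frequent after antibodies develop. The documents do not support that. They give no conversion rate or timing, late detection reverses the direction, and putting never-positive subjects in the before column can reverse it even with early detection.

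A reader might also infer that both rates divide by every subject's whole time at risk. That is literal for EAER only; in EAIR, a subject with an event contributes time only up to that event.

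Finally, the 56- and 72-week figures fit the Q4W/Q4W arm, or bimekizumab-randomized subjects in BKZ Total. SAP 3.6 also presents this set by regimen, and the Q4W/Q8W arm then contributes about 16 weeks to Q4W and, for subjects entering the open-label study, about 40 to Q8W. This changes the size, not the mechanism.

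**Conclusion.** The concern holds for this one table. Followed as written, SAP 10.2.1 and 10.2.2 put events split at positivity over person-time that is not split there, and the resulting rates should not be compared. Under a constant event rate, the false after:before EAER ratio within ever-positive subjects at 56 weeks runs from 6.0 (first positive at Week 8) through 2.5 (Week 16) to 0.56 (Week 36). Neither the size nor the direction in the actual trial can be predicted from the documents.

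The consequence is limited. The table is descriptive, and no test or formal contrast is planned for it. The co-primary and multiplicity-controlled analyses do not use it, and the secondary safety variables are reported in other tables. The change should be made because this is the one planned look at adverse events in relation to antibody formation.

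**What to change.** For this table only, add to SAP 10.2.2:
- The onset categories: before the first confirmed positive sample, on or after it, and never positive. State where subjects positive at baseline belong.
- The date used as first positive. The date already used for the Kaplan-Meier analysis in SAP 9.3.2 is available.
- For EAER, split each subject's time at risk at that date, within regimen where columns are by regimen, and divide each category's events by the time in that category. If before-positive and never-positive subjects share one column, its denominator is the pre-positive time plus all time of never-positive subjects.
- For EAIR, split likewise and restart time to first event at the split.

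The cost is a short SAP clarification and a person-time split in programming, using dates already collected. The split corrects the denominators only. If event rates change with time on treatment, a before/after difference can remain without any antibody effect, and a table footnote should say so.

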10.2.3 Other Safety topics of interest

The following are AEs of other safety topics of interest that require special statistical analyses. Along with the tables described, there will be a table which displays the risk difference and 95% confidence intervals for each of the topics of interest. A corresponding figure (with dot plots) will be prepared.

10.2.3.1 Infections (serious, opportunistic, fungal and TB)

- **Incidence and Event Rate of Serious Infection TEAEs per 100 subject years by SOC, HLT and PT**

Serious infections will be identified based on MedDRA classification (SOC “Infections and infestations”) using the “Any SAE” table. A separate table does not need to be produced to summarize these events.

- **Incidence and Event Rate of Fungal Infection TEAEs per 100 subject years by SOC, HLT and PT**

Fungal infections will be summarized in a stand-alone table. The table will include all TEAEs (serious and non-serious) which code into the High Level Group Term “Fungal infectious disorders”

- **Incidence and Event Rate of Opportunistic Infection TEAEs per 100 subject years by SOC, HLT and PT**

Opportunistic infections (including tuberculosis) will be summarized in a stand-alone table. The table will include all TEAEs identified using UCB-defined search criteria (refer to Excel spreadsheet on “OI - MedDRA v19.0.xlsx” in “Bimekizumab-Safety-Topics-of-Interest.docx”).

The following steps are followed for identifying and reviewing opportunistic infections:

Identification Process

The two steps below outline two ways in which opportunistic infections (or potential opportunistic infections) can be identified:

Step 1: Refer to column B of the spreadsheet which identifies the Preferred Terms (PTs) to be classified as opportunistic infections using either a single ‘x’ or a double ‘xx’.

TEAEs which code to a PT flagged with a single ‘x’ need to also be serious to be considered an opportunistic infection.

All TEAEs which code to a PT flagged with a double ‘xx’ are considered to be an opportunistic infection, regardless of seriousness.

Step 2: Refer to column C of the spreadsheet which identifies the PTs that need to be evaluated on a case-by-case basis by the study physician to determine whether or not it is an opportunistic infection. If Column C has a single ‘x’, then the corresponding preferred term should be flagged for case-by-case review by the study physician.

Review Process

Opportunistic infections for a given study will be reviewed on the following occasions:

At quarterly Infectious Disease Committee (IDC) Meetings, listings will be produced for each study (see details below) and reviewed by the corresponding study physician ahead of the IDC Meeting. These listings will be posted as part of the broader SSD deliverable to a folder named for the given quarter (eg, 2018Q4) on the SharePoint. They should be based on the same data cut as the one used for SSD and should be delivered at the same time as the SSD outputs. The IDC will then agree on the final adjudication for each potential opportunistic infection.

For each study, a final listing for opportunistic infections (in the format described below) will be produced and agreed upon between the study physician and the IDC prior to finalizing the database.

In each of the circumstances described above, the study programming team will produce an Excel listing that will be provided to the project lead statistician, project lead programmer, and to the study physician (who will subsequently provide it to the IDC). The Excel listing will contain the following columns (using the descriptions below as the column headings in the Excel listing):

Study ID
Unique Subject ID
AE Term (Verbatim)
AE Preferred Term
AE System Organ Class
AE High Level Term
AE Low Level Term
Date of Onset
Outcome of Adverse Event
Date of Outcome
TEAE Flag
Serious Adverse Event?
Relationship to Study Medication
Intensity
Action Taken with IMP
Opportunistic Infection – Automatic
Opportunistic Infection – Manual Review
Flag
Data Cut Date
Opportunistic Infection – Final Adjudication

Note the following about the final 5 variables in this listing:

Opportunistic Infection – Automatic: This is flagged as “Y” if the criteria for automatic selection as described in “Step 1” of the identification process are met.

Opportunistic Infection – Manual Review: This is flagged as “Y” if the criteria for case-by-case selection as described in “Step 2” of the identification process are met.

Flag – This has a value of either “NEW” or “OLD”. It is marked as “NEW” if the event is appearing for the first time in that run of the listing. Otherwise, if it has appeared previously, it is marked as “OLD”. Unique records are determined by USUBJID AESPID for purposes of identifying whether an event has been modified from a previous run.

Date – Only for cases where Flag is “NEW”, this field will be populated with the data cut date for that particular run of the listing.

Opportunistic Infection – Final Adjudication – For new events, this is always left blank by the programmers. It should be completed by the study physician/IDC for every event that appears in the listing. For events adjudicated as opportunistic, the field should be populated with a “Y”. Following each review by the study physician and IDC, the Opportunistic Infection – Final Adjudication column will be completed (as described above), and the spreadsheets for each study will be returned to the study programming team via e-mail (coordinated by the IDC secretary). Then, for subsequent runs of the listing, the study programming teams will incorporate adjudications from previous runs.

10.2.3.2 Malignancies

- **Incidence and Event Rate of Malignancy (including Unspecified Tumours) TEAEs per 100 subject years by SOC, HLT and PT**

This table will be based on the criteria Standardized MedDRA Query (SMQ) = “Malignant or unspecified tumours (SMQ)”

- **Incidence and Event Rate of Malignancy TEAEs per 100 subject years by SOC, HLT and PT**

This table will be based on the criteria SMQ = ”Malignant tumours (SMQ)”.

SMQ search should include all TEAEs which code to a PT included in the Scope=Narrow group within each SMQ.

Note that the events included in the “Malignant tumours” table will be a subset of the events included in the “Malignant or unspecified tumours” table. While the “Malignant tumours (SMQ)” is most relevant, “Malignant or unspecified tumours (SMQ)” must be reviewed for potential malignancies.

The output table based on the SMQ=”Malignant or unspecified tumours (SMQ)” will include 2 different overall incidence rows:

- The first overall incidence row will summarize “Any malignancies (including unspecified)” and this row will summarize the incidence of all TEAEs flagged for inclusion in the table, regardless of the High Level Term (HLT) it codes to.
- The second overall incidence row will summarize “Any malignancy (including unspecified, excluding non-melanomic skin cancers)” and this row will summarize the incidence of AEs flagged for inclusion in the table, excluding those which code to an HLT of “skin neoplasms malignant and unspecified (excl melanoma)”.

10.2.3.3 Major adverse cardiac events (MACE)

- **Incidence and Event Rate of Major Cardiac Event (MACE) TEAEs per 100 subject years by SOC, HLT and PT**

Major adverse cardiac events (MACE) will be presented in a table. The classification of an event as MACE is determined by an external cardiovascular event adjudication committee.

A separate table and listing will present the adjudicated cardiovascular events by type. For each cardiovascular event type (24 total), the individual PTs which fall within each event type will be summarized.

Additionally, a listing of all events identified for potential review by the cardiovascular event adjudication committee will be produced. This listing will indicate whether each event was escalated to the committee for formal review/adjudication.

